5.2 PARTICIPANT EXCLUSION CRITERIA

Subjects who meet at least one exclusion criteria will not be able to participate in the study.

Exclusion criteria:

1. Participants who have received any anticancer treatment (including Chinese herbal medicine specified for the treatment of tumor) within 21 days or any investigational agent within 30 days prior to the first dose of study drug. This does not apply to the use of TSH-suppressive thyroid hormone therapy.
2. Major surgery within 21 days prior to the first dose of study drug.
3. Palliative radiation therapy within 14 days prior to the first dose of study drug.
4. Participants having > 30 mg/dL urine protein on urine dipstick testing (Participants with urine protein < 1 g/24 hour (h) will be eligible).
5. Gastrointestinal malabsorption or any other condition that in the opinion of the investigator might affect the absorption of Lenvatinib, Sorafenib, Cabozantinib, or Vandetanib.
6. Significant cardiovascular impairment: history of (a) congestive heart failure greater than New York Heart association (NYHA) Class II, (b) unstable angina, (c) myocardial infarction, (d) stroke, or (e) cardiac arrhythmia associated with impairment within 6 months of the first dose of study drug.
7. Bleeding or thrombotic disorders (Treatment with low molecular weight heparin is allowed).
8. Radiographic evidence of major blood vessel invasion/infiltration.
9. Active hemoptysis (bright red blood of at least 0.5 teaspoon) within 21 days prior to the first dose of study drug.
10. Active infection (any infection requiring systemic treatment).
11. Active malignancy (except for DTC/MTC or definitively treated basal or squamous cell carcinoma of the skin, or carcinoma in-situ of the cervix or bladder) within the past 24 months.
12. Known intolerance to any of the study drugs (or any of the excipients).
13. Any medical or other condition which, in the opinion of the investigator, would preclude

- participation in a clinical trial.
14. Females who are pregnant or breastfeeding.
 15. Participants who are taking prohibited medications outlines in section 7.5.

5.3 STRATEGIES FOR RECRUITMENT AND RETENTION

Patients with metastatic progressive thyroid cancer (DTC and MTC) referred to medical oncologist clinic for systemic therapy will be screened based on inclusion and exclusion criteria. Subjects who meet inclusion criteria and are willing to participate in the study will be enrolled.

No compensation will be provided for study participation.

5.4 PARTICIPANT WITHDRAWAL OR TERMINATION

5.4.1 REASONS FOR WITHDRAWAL OR TERMINATION

Participants are free to withdraw from participation in the study at any time upon request.

An investigator may terminate participation in the study in the following circumstances:

- If any treatment-related Grade 4 adverse events (AE) develops during TKIs therapy.
- If any clinically adverse event (AE), laboratory abnormality, or other medical condition or situation occurs such that continued participation in the study would not be in the best interests of the participant
- If the participant meets any exclusion criteria (either newly developed or not previously recognized) that precludes further study participation.
- Extraordinary medical circumstances: If at any time the constraints of this protocol are detrimental to the patient's health, the protocol treatment should be discontinued.
- If patient develops progressive disease, then the patient will discontinue the protocol therapy (See Appendix 4).
- If patient develops unacceptable toxicity, then the patient will discontinue the protocol therapy.

The reason and date for patient removal from the study must be documented in the Case Report Form (CRF).

5.4.2 HANDLING OF PARTICIPANT WITHDRAWALS OR TERMINATION

Every effort will be made to undertake protocol-specified safety follow-up procedures to capture AEs, serious adverse events (SAEs), and unanticipated problems.

Those who discontinue protocol therapy early will be followed for response until progression and for survival for 1 year from the date of withdraw or termination.

Patients removed from study for unacceptable adverse events will be followed until resolution or stabilization of the adverse event.

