- Patients in the adaptive therapy regimen will receive TKI therapy in cycles: continuous treatment at the indicated dose until the patients' tumor marker (thyroglobulin in DTC patients; calcitonin or CEA in MTC patients) drops by $\geq 50\%$ from the level at the time of enrollment ("baseline" level). Only tumor markers that meet inclusion criteria at baseline can be used for randomization and adaptive therapy purposes. A new cycle of TKI treatment will begin:
 - - When/if the tumor marker increases to $\geq 70\%$ of the "baseline" level.
OR
 - At the discretion of the treating physician if a patient develops worsening disease-related symptoms with rising tumor marker levels indicating disease progression. In the case of resumption for disease-related symptoms, TKI treatment will continue until the symptoms improve at the discretion of the treating physician and the tumor markers are again $\leq 50\%$ from the level at the time of enrollment.

Study Duration: 48 months

Participant Duration: 48 months

SCHEMATIC OF STUDY DESIGN

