All study participants will be followed for at least 24 months after treatment initiation. Patients will continue to receive treatment until confirmed disease progression, development of unacceptable toxicity, withdrawal of consent, or study termination by investigator. After disease progression, subjects will be followed for survival and may be treated according to standards of care, which includes conventional (continuous) TKI treatment for patients in the adaptive therapy arm.

After 24 months, patients in the adaptive therapy arm that remain on TKI therapy and under control will be given the choice to continue with adaptive therapy or to convert to conventional (continuous) regimen, which is the current standard of care.

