4.2 STUDY ENDPOINTS

4.2.1 PRIMARY ENDPOINT

The primary endpoint is time to TKI treatment discontinuation due to progressive disease, intolerability (Grade 3 and 4 toxicities refractory to best symptom management that are deemed probably or definitely related to study treatment only), or disease-related death at 2 years. We hypothesize that time on TKI treatment will be significantly longer for patients on the adaptive therapy arm than on the conventional therapy arm because we expect a decrease in drug-associated toxicities and a delay in the selection of resistant clones in the adaptive therapy arm.

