6.1.8 DOSE ADJUSTMENTS/MODIFICATIONS/DELAYS

All patients will start receiving standard of care treatment:

- DTC: Lenvatinib 24 mg daily or Sorafenib 400 mg twice daily
- MTC: Cabozantinib 140 mg daily or Vandetanib 300 mg daily.

Dose will be adjusted as needed due to toxicity or drug tolerance in both arms (See below).

- Patients in the conventional therapy regimen (“responders” and non-responders”) will receive continuous (daily) treatment at the indicated dose.

- Patients in the adaptive therapy regimen will receive TKI therapy in cycles: continuous (daily) treatment at the indicated dose until the patients’ tumor marker (thyroglobulin in DTC patients; calcitonin or CEA in MTC patients) drops by $\geq 50\%$ from the level at the time of enrollment (“baseline” level). Only tumor markers that meet inclusion criteria at baseline can be used for randomization and adaptive therapy purposes. A new cycle of TKI treatment will begin:

1. When/if the tumor marker increases to $\geq 70\%$ of the “baseline” level.

OR

2. At the discretion of the treating physician if a patient develops worsening disease-related symptoms with rising tumor marker levels indicating disease progression. In the case of resumption for disease-related symptoms, TKI treatment will continue until the symptoms improve at the discretion of the treating physician and the tumor markers are again $\leq 50\%$ from the level at the time of enrollment.

All study participants will continue to receive treatment until confirmed disease progression, development of unacceptable toxicity, withdrawal of consent, or study termination by investigator.

After disease progression subjects will be followed for survival and may be treated according to standards of care, which includes conventional (continuous) TKI treatment for patients in the adaptive therapy arm.

Held doses will be considered missed and will not be made up so that patients will complete on-study treatment within the anticipated 24 month duration. Treatment may be delayed for toxicity, other palliative treatments (i.e. palliative radiation, palliative surgery, etc.) for a maximum of 4 weeks. Any treatment beyond the 24 months specified herein will be considered off protocol and not subject to the requirements of this protocol.

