7.3.3 FOLLOW-UP

Follow-up Visits

Study participants will be seen weekly for the first cycle (Cycle 1 Days 8, 15 and 22), every two weeks for the second cycle (Cycle 2 Days 1, 15), every four weeks until cycle 12 (Day 1 of Cycles 3-12); and every 2 cycles thereafter until end of study (Day 1 of cycles 14, 16, 18, 20 and 24). However, when the patient is off the TKI with observation only in the adaptive arm, the patient needs to follow up every 28 days (+/- 7 days) for determination of starting a new cycle.

In each scheduled visit we will:

- Obtain vital signs.
- Record all concomitant medication use.
- Perform a comprehensive physical examination.
- Evaluate ECOG performance status.
- Obtain laboratory tests and urinary dipstick.
- Assess for AEs and SAEs.
- Assess compliance with the medication.
- Assess survival.

Thyroid panel evaluation

Thyroid panel will be assessed every 2 weeks during the first two cycles (Cycle 1 Day 15, Cycle 2 Day 1, Cycle 2 Day 15, and Cycle 3 Day 1). If the tumor marker (thyroglobulin in DTC patients; calcitonin or CEA in MTC patients) drops by $\geq 50\%$ from baseline (Cycle 1 Day 1) during the first two cycles (analysis of Cycle 3 Day 1 included), the patient will be randomized to receive either standard (continuous) or adaptive (intermittent) therapy. Patients randomized to

the standard therapy arm will then get Thyroid panel checked every 3 cycles (Day 1 of Cycle 6, 9, 12). Patients randomized to the adaptive therapy arm will get Thyroid panel checked every cycle (Day 1) during the first two years. After 24 months, patients in the adaptive therapy regimen who remain on TKI therapy will be given the choice to continue with the adaptive therapy regimen and monitoring of the thyroid panel in every cycle; or to convert to standard (continuous) regimen in which case thyroid panel evaluation will be checked every 3 cycles. In either case, all patients that continue to receive TKI therapy beyond 24 months will be treated off trial. Patients in which the tumor marker does not drop $\geq 50\%$ within the first two months of TKI therapy will be managed by the standard of care.

Diagnostic imaging

Diagnostic imaging of affected and suspected sites (CT and/or MRI) will be done at Day 1 of cycles 3, 6, 9, 12, 16, 20, 24 in all patients. Diagnostic imaging will continue to be done every 4 months thereafter while the patient remains on TKI therapy or as clinically indicated otherwise.

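### Section 5.4.2 ends survival follow-up 1 year after early discontinuation, against the 24-month minimum in 4.1, and ties overall survival censoring to stopping therapy

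*Combined protocol and SAP*

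**What the plan says.** Section 5.4.2 deals with patients who come off protocol treatment ahead of plan. Its rule for them is "followed for response until progression and for survival for 1 year from the date of withdraw or termination". It makes no exception by reason for stopping. Section 5.4.1, directly above it, lists both progression ("If patient develops progressive disease, then the patient will discontinue the protocol therapy") and unacceptable toxicity as reasons to discontinue.

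Other sections give different follow-up:

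- Section 4.1 sets a minimum for everyone: "All study participants will be followed for at least 24 months after treatment initiation".
- Section 4.1 also says "After disease progression, subjects will be followed for survival", with no end date. Section 6.1.8 repeats this: "After disease progression subjects will be followed for survival and may be treated according to standards of care".
- The study summary gives "Participant Duration: 48 months".
- Section 10.4 assumes 2 years of uniform accrual and a 2-year minimum follow-up.
- Section 7.3.4 assesses survival at a final visit at least 24 months after TKI start.

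OS is a secondary endpoint (4.2.2). Section 10.3.2 estimates its median by Kaplan-Meier with a Greenwood interval, and states no OS censoring rule.

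**The concern.** Two sections prescribe different survival follow-up for the same patients, so staff working from 5.4.2 and staff working from 4.1 would produce different OS data. The patients affected are not a fringe group. Progression and intolerable toxicity are the main ways to reach the primary endpoint, so on its face 5.4.2 covers ordinary treatment failures.

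There is also a statistical problem. Kaplan-Meier assumes that censoring tells us nothing about prognosis. Under 5.4.2 the censoring date is the discontinuation date plus 12 months. Discontinuation is probably related to the risk of death, and the trial expects its timing to differ between arms. Follow-up that was never done may not be recoverable at analysis. In arms of 12 and 24, each missing death counts.

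**Working it through.** **The plan's own figure.** Section 10.4 claims 82% power at HR 0.50 (67% at HR 0.6) with 24 and 12 patients and one-sided alpha 0.20. Exponential times with 24 months' uniform accrual and 24 months' minimum follow-up give 10.4 + 15.3 = 25.7 expected events. The power is Φ(|ln 0.5| / √(1/10.4 + 1/15.3) − 0.84) = 81%, and 67.5% at HR 0.6. Both agree with the plan. The event here is discontinuation itself, so the 1-year rule does not change this power.

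**The conflict in dates.** Let T be the month of stopping. Section 5.4.2 ends survival follow-up at T + 12, and 4.1 requires at least 24. T + 12 < 24 exactly when T < 12. Stopping at month 3, 6 or 9 ends follow-up at month 15, 18 or 21. For patients who stop because of progression, 4.1 and 6.1.8 set no end date, so the sections conflict whenever they stop.

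**How many stop before month 12.** Using the plan's medians of 12 and 24 months:

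- Conventional: 1 − 0.5^(12/12) = 0.500, or 6.0 of 12.
- Adaptive: 1 − 0.5^(12/24) = 0.293, or 7.0 of 24.

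These are upper bounds, because discontinuation events include deaths (4.2.1: "or disease-related death at 2 years"). The clock may also start at randomization, which falls at about month 2 at the latest (7.3.3: "during the first two cycles (analysis of Cycle 3 Day 1 included), the patient will be randomized"). The shares are then 1 − 0.5^(10/12) = 0.439 (5.3 of 12) and 1 − 0.5^(10/24) = 0.251 (6.0 of 24).

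**Consequence for OS.** The documents give no death hazards. *Assumption:* no deaths on therapy, exponential survival after stopping with median m = 12, 18 or 24 months, and all early stops covered by 5.4.2.

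- Censored alive before month 24 is P(T < 12) × 0.5^(12/m).
- Deaths before month 24 that go unobserved are the integral over stopping times u from 0 to 12 of f(u) × 0.5^(12/m) × [1 − 0.5^((12−u)/m)], where f is the density of T.
- The remaining rows are simulated and compare 5.4.2 with a common cut-off giving 24 to 48 months of follow-up.

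| Results for m = 12 / 18 / 24 | Conventional (n = 12) | Adaptive (n = 24) |
|---|---|---|
| Censored alive before month 24 | 3.0 / 3.8 / 4.2 | 3.5 / 4.4 / 5.0 |
| Deaths before month 24 unobserved | 0.92 / 0.83 / 0.73 | 1.03 / 0.93 / 0.81 |
| All deaths before month 24 | 4.84 / 3.71 / 3.00 | 6.00 / 4.57 / 3.68 |
| Deaths observed, 5.4.2 | 4.92 / 3.63 / 2.88 | 7.02 / 5.18 / 4.10 |
| Deaths observed, common cut-off | 7.25 / 5.92 / 4.97 | 9.93 / 8.01 / 6.69 |
| Deaths lost | 32 / 39 / 42% | 29 / 35 / 39% |
| Median OS reached, 5.4.2 | 62 / 39 / 28% | 29 / 15 / 9% |
| Median OS reached, common cut-off | 90 / 73 / 54% | 57 / 33 / 20% |
| Bias of 24-month OS (points) | +4.1 / +3.6 / +3.1 | +3.1 / +2.8 / +2.4 |

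The sampling SD of 24-month OS under 5.4.2 is 13 to 15 points (conventional) and 7 to 9 points (adaptive).

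**Sensitivity.** If only 30% of stops fall under 5.4.2 (assumed), 9% to 13% of deaths are lost and the bias is about +1 point. Allowing deaths on therapy, with all stops covered:

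| Median survival in months, on therapy / after stopping | 24-month bias, conventional / adaptive (points) | Deaths lost, conventional / adaptive |
|---|---|---|
| 60 / 18 | +2.2 / +1.7 | 30% / 21% |
| 48 / 24 | +1.4 / +1.1 | 29% / 19% |
| 36 / 36 | 0 / 0 | 25% / 15% |
| 60 / fourfold hazard in the first year off therapy only | −2.4 / −0.8 | 12% / 8% |

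The sign of the bias changes across these patterns. The loss of deaths does not.

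**The case against.** Four points can be made for the plan.

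1. **The larger losses depend on the comparator.** No section names a 24-to-48-month OS cut-off; it is built from the accrual assumption in 10.4. If 5.4.2 is merely raised to the later of month 24 or T + 12, only 0.7 to 1.0 death per arm is restored. The chance of reaching the median rises by roughly 1 to 9 points (conventional to 71 / 46 / 31%, adaptive to 34 / 17 / 10%), and the 24-month bias disappears. This stands: most of the 29% to 42% reflects longer follow-up rather than the 24-month conflict alone. But that smaller repair leaves censoring tied to discontinuation after month 24. Under the same assumption the 36-month estimate is still about 5 to 6 points too high. Sections 4.1 and 6.1.8 also already promise open-ended survival follow-up for patients who progress.

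2. **A narrower reading is possible.** The words about response until progression could confine 5.4.2 to patients who have not progressed. The effect is then nearer the 30% case. The plan does not say so, and patients who stop for toxicity or by choice before month 12 would still fall short of 4.1.

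3. **The bias cannot be derived from the documents.** This is correct. It may be positive, zero or negative, and it is small against sampling error.

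4. **OS is secondary and descriptive.** This is also correct: no OS test is planned. Even with a common cut-off, the adaptive median is reached in only 20% to 57% of simulated arms.

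**Conclusion.** The concern holds. The contradiction between 5.4.2 and 4.1 for stops before month 12 is exact and needs no assumption. On the plan's medians it affects up to 50% of conventional and 29% of adaptive patients.

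The effect on OS rests on assumed hazards and on how widely 5.4.2 is read. With all stops covered, no deaths on therapy and 12 to 24 months' median survival after stopping, about one death per arm before month 24 is lost (17% to 24% of deaths by then). Across the other hazard patterns tried with all stops covered, 8% to 30% of deaths are lost against the common cut-off. The loss of information is the firm consequence; the size and direction of bias are not. Neither the time-to-discontinuation analysis nor its stated power is affected. The plan should be corrected, but this does not undermine the trial's main comparison.

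**What to change.** Replace the 1-year limit in 5.4.2 with one survival follow-up rule, worded identically in 4.1, 5.4.2, 6.1.8 and the study summary. It should cover all enrolled participants (about 45, including the roughly 9 not randomized), whenever and for whatever reason therapy stops. Follow-up would run until death, withdrawal of consent to follow-up, or one common study cut-off.

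A cut-off 24 months after the last participant starts TKI fits the 2-year accrual and 2-year minimum follow-up in 10.4. It gives 24 to 48 months per person, so the 48 months in the summary should be worded as a maximum.

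In 10.3.2, state that OS is censored only at that cut-off, at withdrawal of consent to follow-up, or at loss to follow-up. Table 8 should also show survival contacts after the end-of-treatment visit, since none is scheduled there now.

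The cost is amendment wording plus periodic vital-status checks, by phone or from records, at one site. The change concerns follow-up only and leaves treatment as it is.

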5.5 PREMATURE TERMINATION OR SUSPENSION OF STUDY

This study may be temporarily suspended or prematurely terminated by the investigators. Circumstances that may warrant termination or suspension include, but are not limited to:

- Determination of unexpected, significant, or unacceptable risk to participants.
- Demonstration of efficacy that would warrant stopping.
- Insufficient compliance to protocol requirements.
- Data that is not sufficiently complete and/or evaluable.
- Determination of futility.

If the study is prematurely terminated or suspended, the PI will promptly inform the IRB and will provide the reason for the termination or suspension.

Study may resume once concerns about safety, protocol compliance, data quality are addressed and satisfy the PI and IRB.

6. STUDY AGENT

6.1 STUDY AGENT(S) AND CONTROL DESCRIPTION

6.1.1 ACQUISITION

Tyrosine kinase inhibitors used in this study, Lenvatinib, Sorafenib, Cabozantinib, and Vandetanib, are FDA- approved and standard of care for DTC and MTC. They will be prescribed through specialty pharmacy or conventional pharmacy depending on the availability. The study participants will be mailed to home or personally pick up the medication depending on the availability.

6.1.2 FORMULATION, APPEARANCE, PACKAGING, AND LABELING

Lenvatinib is an FDA approved drug for treatment of metastatic progressive differentiated thyroid cancer. Lenvatinib capsules (Lenvima) are produced by Eisai and come in 2 strengths: 10 mg and 4 mg; capsules are supplied in cartons of 6 blister cards. Each cartoon contains a 30 day supply of Lenvatinib capsules.

Sorafenib is an FDA approved drug for treatment of metastatic progressive differentiated thyroid cancer. Sorafenib (Nexavar) is produced by Bayer in 200 mg tablets.

Cabozantinib is an FDA approved drug for treatment of metastatic progressive medullary thyroid cancer. Cabozantinib (Cometriq) is produced by Exelixis as 80 mg and 20 mg gelatin capsules.

Vandetanib is an FDA approved drug for treatment of metastatic progressive medullary thyroid cancer. Vandetanib (Caprelsa) is produced by Sanofi Genzyme in 2 strengths: 100 mg and 300 mg tablets.

6.1.3 PRODUCT STORAGE AND STABILITY

Lenvatinib, Sorafenib, Cabozantinib, and Vandetanib must be stored in accordance with the instructions on the label at room temperature: 68 F to 77 F (20 C to 25 C).

6.1.4 PREPARATION

No specific preparation of study agent is required.

6.1.5 DOSING AND ADMINISTRATION

Study participants with DTC will be taking either:

- **Lenvatinib** (Lenvima) 24 mg in the form of two 10-mg capsules and one 4-mg capsule. Lenvatinib should be taken at the same time each day. If the patient misses a dose and it cannot be taken within 12 hours, then that dose should be skipped and the next dose should be taken at the usual time of administration. Lenvatinib may be taken in a fasting state or following a meal. Lenvatinib capsules can be swallowed whole. Alternatively, the capsules can be dissolved in one tablespoon of liquid (water or apple juice). Leave the capsule in the liquid for at least 10 minutes. Stir for at least 3 minutes. Drink the mixture and add another tablespoon of liquid (water or apple juice) to the glass, swirl the contents a few times and swallow the additional liquid.

Or

- **Sorafenib** (Nexavar) 400 mg twice daily in the form of two 200-mg tablets every 12 hours, on empty stomach (at least 1 hour before and 2 hours after a meal). If the patient misses a dose, the next dose should be taken at the regularly scheduled time, and not double the dose.

Study participants with MTC will be taking either:

- **Cabozantinib** (Cometriq) 140 mg once daily in the form of one 80-mg capsule and three 20-mg capsules. Cabozantinib should be taken at the same time each day, on empty stomach (at least 1 hour before and 2 hours after meal) with at least 8 ounces of water. If the patient misses a dose and it cannot be taken within 12 hours, then that dose should be skipped and the next dose should be taken at the usual time of administration.

Or

- **Vandetanib** (Caprelsa) 300 mg once daily in the form of one 300-mg tablet. Vandetanib should be taken at the same time each day. If the patient misses a dose and it cannot be taken within 12 hours, then that dose should be skipped and the next dose should be taken at the usual time of administration. Vandetanib may be taken with or without food. Tablets can be dispersed in 2 ounces of water by stirring for approximately 10 minutes (will not dissolve completely). Do not use other liquids for dispersion. Swallow immediately after dispersion and mix any remaining residue with 4 additional ounces of water and swallow.

